## 8.3. Safety Assessments

Planned time points for all safety assessments are provided in the SoA. Unscheduled safety measurements may be obtained at any time during the study to assess any perceived safety issues.

#### 8.3.1. Physical Examinations

A complete physical examination will include, at a minimum, head, ears, eyes, nose, mouth, skin, heart and lung examinations, lymph nodes, and gastrointestinal, musculoskeletal, and neurological systems.

A brief physical examination will include, at a minimum, assessments of general appearance, the respiratory and cardiovascular systems, and participant-reported symptoms.

Complete physical examinations will be done at the time points specified in the SoA otherwise, brief examinations if findings during a previous examination or new/open AEs, if appropriate at Investigator discretion.

Physical examinations may be conducted by a physician, trained physician's assistant, or nurse practitioner as acceptable according to local regulation.

Height and weight will also be measured and recorded as per the SoA. For measuring weight, a scale with appropriate range and resolution is used and must be placed on a stable, flat surface. Weight will be recorded using a calibrated scale (with the same scale used if possible, for the duration of the study) reporting weight in either pounds (lb) or kilograms (kg), and accuracy to the nearest 0.2 lb (or 0.1 kg); ie, the device must be able to distinguish a difference between 150.4 lb (68.4 kg) versus 150.2 lb (68.3 kg).

Weight measurement should be taken under the following conditions:

- In the morning in a fasting state.
- After void of urine.
- After removal of shoes, bulky layers of clothing and jackets so that only light clothing remains.
- After removal of pocket contents.
- While remaining still during the measurement.

Physical examination findings collected during the study will be considered source data and will not be required to be reported, unless otherwise noted. Any untoward physical examination findings that are identified during the active collection period and meet the definition of an AE or SAE (Appendix 3) must be reported according to the processes in Sections 8.4.1 to 8.4.3.

## 8.3.2. Vital Signs

#### 8.3.2.1. Blood Pressure and Pulse Rate

Vital signes (systolic BP, diastolic BP and PR) will occur as specified in the SoA. Supine BP will be measured with the participant's arm supported at the level of the heart and recorded to the nearest mm Hg after approximately 5 minutes of rest. The same arm (preferably the dominant arm) will be used throughout the study. Participants should be instructed not to speak during measurements. If triplicate measurements are obtained, they should be collected approximately 2 minutes apart.

At Screening, the participant's arm circumference should be measured (e.g., using a flexible anthropometric tape) at the midpoint of the length of the upper arm and the appropriate cuff selected and used throughout the study. The same properly sized and calibrated BP cuff will be used to measure BP each time.

The use of an automated device for measuring BP and pulse rate is acceptable; however, when done manually, pulse rate will be measured in the brachial/radial artery for at least 30 seconds. When the timing of these measurements coincides with a blood collection, BP and pulse rate should be obtained prior to the nominal time of the blood collection.

Additional collection times, or changes to collection times, of BP and pulse rate will be permitted, as necessary, to ensure appropriate collection of safety data.

Any untoward vital sign findings that are identified during the active collection period and meet the definition of an AE or SAE (Appendix 3) must be reported according to the processes in Sections 8.4.1 to 8.4.3.

## 8.3.2.2. Temperature

Body temperature will be measured at the timepoints listed in the SoA. Temperature will be measured orally. No eating, drinking, or smoking is allowed for 15 minutes prior to the measurement.

#### 8.3.3. Electrocardiograms

Standard 12-lead ECGs utilizing limb leads (with a 10-second rhythm strip) should be collected at times specified in the SoA section of this protocol using an ECG machine that automatically calculates the HR and measures PR interval, QT interval, QTcF, and QRS complex. Alternative lead placement methodology using torso leads (eg, Mason-Likar) is not recommended given the potential risk of discrepancies with ECGs acquired using standard limb lead placement. All scheduled ECGs should be performed after the participant has rested quietly for at least 5 minutes in a supine position.

To ensure safety of the participants, a qualified individual at the investigator site will make comparisons to baseline measurements. Additional ECG monitoring will occur if a) a postdose QTcF interval is increased by ≥60 ms from the baseline **and** is >450 ms; or b) an absolute QT value is ≥500 ms for any scheduled ECG. If either of these conditions occurs, then 2 additional ECGs will be collected approximately 2 to 4 minutes apart to confirm the original measurement. If the QTcF values from these repeated ECGs remain above the threshold value, then a single ECG must be repeated at least hourly until QTc values from 2 successive ECGs fall below the threshold value that triggered the repeat measurement.

If a) a postdose QTcF interval remains  $\ge 30$  ms from the baseline and is > 450 ms; or b) an absolute QT value is  $\ge 500$  ms for any scheduled ECG for greater than 4 hours (or sooner, at the discretion of the investigator); or c) QTcF value get progressively longer, the participant should undergo continuous ECG monitoring.

In some cases, it may be appropriate to repeat abnormal ECGs to rule out improper lead placement as contributing to the ECG abnormality. It is important that leads be placed in the same positions each time in order to achieve precise ECG recordings. If a machine-read QTc value is prolonged, as defined above, repeat measurements may not be necessary if a qualified medical provider's interpretation determines that the QTcF values are in the acceptable range.

ECG values of potential clinical concern are listed in Appendix 8.

## 8.3.4. Clinical Safety Laboratory Assessments

See Appendix 2 for the list of clinical safety laboratory tests to be performed and the SoA for the timing and frequency. All protocol-required laboratory assessments, as defined in Appendix 2, must be conducted in accordance with the laboratory manual and the SoA. Unscheduled clinical laboratory measurements may be obtained at any time during the study to assess any perceived safety issues.

The investigator must review the laboratory report, document this review, and record any clinically significant changes occurring during the study in the AE section of the CRF. Clinically significant abnormal laboratory test findings are those that are not associated with the underlying disease, unless judged by the investigator to be more severe than expected for the participant's condition.

All laboratory tests with values considered clinically significant and abnormal during participation in the study or within 28-35 days after the last dose of study intervention should be repeated until the values return to normal or baseline or are no longer considered clinically significant by the investigator or study medical monitor.

If such values do not return to normal/baseline within a period of time judged reasonable by the investigator, the etiology should be identified and the sponsor notified.

See Appendix 6 for suggested actions and follow-up assessments in the event of potential DILI.

See Appendix 7 for instructions for laboratory testing to monitor kidney function and reporting laboratory test abnormalities.

Participants may undergo random urine drug testing at the discretion of the investigator. Drug testing conducted prior to dosing must be negative for participants to receive study intervention.

## 8.3.5. COVID-19 Specific Assessments

Participants will be screened for COVID-19 according to local procedures prior to being admitted to the clinic for confinement in Period 1. Subsequent testing will also be done according to local procedure, if participants develop symptoms suggestive of COVID-19. If a participant tests positive for SARS-CoV-2 infection, they will be discharged from the study.

## 8.3.6. Management of Hypoglycemia

While hypoglycemia is not expected in the study participants, fasting blood glucose will be measured as part of laboratory assessment per the SoA. In addition, as a precaution, participants will be monitored for the signs and symptoms associated with hypoglycemia.

Any episode of hypoglycemia must be captured on the HAE CRF with specific details captured on the HAE Form CRF. For the definition of a hypoglycemic episode and severity categorization see Section 8.3.6.1 below.

For medical management of hypoglycemia, the investigator may administer oral carbohydrate, glucagon, or IV glucose according to his or her medical judgment.

## **8.3.6.1.** Definition and Severity of Categorization of Hypoglycemic Adverse Event (HAE)

The investigator must assess the glucose values reported by the central/local laboratory, as well as any signs or symptoms reported by the study participant.

HAE is defined as **one** of the following:

- a. Asymptomatic hypoglycemia: An event not accompanied by typical symptoms of HAE but a glucose value of <70 mg/dL (3.9 mmol/L) using either glucometer (fingerstick blood glucose) at the study site or sponsor-identified central/local laboratory (blood glucose).
- b. Documented symptomatic hypoglycemia: An event during which typical symptoms of HAE are accompanied with a glucose value of <70 mg/dL (3.9 mmol/L), using glucometer at the study site or sponsor identified central/local laboratory, and the clinical picture includes prompt resolution with food intake, subcutaneous glucagon, or IV glucose.

c. Probable symptomatic hypoglycemia: An event during which symptoms of HAE are not accompanied by a glucose determination but was presumably caused by a glucose concentration of <70 mg/dL (3.9 mmol/L), and the clinical picture includes prompt resolution with food intake, subcutaneous glucagon, or IV glucose.

Each episode of HAE must be categorized with respect to severity. In order to characterize the event as severe, all 3 criteria below must be met:

- 1. The participant was unable to treat him/herself. Neurologic impairment, and not the age of the participant, is the explanation for why the participant could not treat him/herself and required the assistance of another person.
- 2. The participant exhibited at least 1 of the following neurological symptoms:
  - Memory loss.
  - Confusion.
  - Uncontrolled behavior.
  - Irrational behavior.
  - Unusual difficulty in awakening.
  - Suspected seizure.
  - Seizure.
  - Loss of consciousness.

#### 3. Either:

- If blood glucose was measured and was ≤54 mg/dL (2.7 mmol/L) using glucometer (or central/local laboratory) or
- If blood glucose was not measured, the clinical manifestations were reversed by oral carbohydrates, subcutaneous glucagon, or IV glucose.

Events that do not meet all the criteria above for severe HAE are characterized as mild or moderate in severity.

#### 8.3.6.2. Glucometer Monitoring of Glucose

Monitoring of FSBG using glucometer measurements is not required per protocol but may be obtained if the investigator or participant notes symptoms of hypoglycemia.

If obtained, FSBG readings will be maintained at the CRU in source documents, and only the glucose results from the laboratory will be reported in the study database.

If an FSBG result is  $\leq$ 70 mg/dL, a second FSBG should be obtained to confirm the glucose value, in addition to a venous sample that will be sent to the clinical laboratory for confirmation. If the value from this second FSBG is also  $\leq$ 70 mg/dL, the second value will be recorded as a hypoglycemic AE. FSBG will continue to be monitored until the glucose value returns to  $\geq$ 70 mg/dL. Samples may be taken more frequently if deemed necessary by the investigator.

### 8.3.7. Pregnancy Testing

A serum pregnancy test is required at screening. Following screening, pregnancy tests may be urine or serum tests, and must have a sensitivity of at least 25 mIU/mL. Pregnancy tests will be performed in WOCBP at the times listed in the SoA. Following a negative pregnancy test result at Screening, appropriate contraception must be commenced and a second negative pregnancy test result will be required at the baseline visit prior to the participant's receiving the study intervention. Pregnancy tests will also be done whenever 1 menstrual cycle is missed during the active treatment period (or when potential pregnancy is otherwise suspected) and at the end of the study. Pregnancy tests may also be repeated if requested by IRBs/ECs or if required by local regulations. If a urine test cannot be confirmed as negative (eg, an ambiguous result), a serum pregnancy test is required. In such cases, the participant must be excluded if the serum pregnancy result is positive.

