PF-07081532 administration f					X	X	X	1	Table 5	Table 4
PF-07081532 PK										
Rosuvastatin PK				Table 4	Xg					1
Dabigatran PK			Table 3	1 1				Table 3		
CCI										
Blood Sampling for:h										
- Chemistry	X	X					X			
- Calcitonin, amylase, lipase	X	X					X			
- Free T4, TSH, lipid panel, total bile acids	X	X	_							
- Hematology/ HbA1c	X	X					X			
- FSH i , HIV, HBsAg, HCVAb, HCV RNA, C-peptide	X									
- PT/INR	X									
- Serum pregnancy test i	X	X								
CCI										
Urine Sampling for:										
- Urine drug test k	X	X								
- Urinalysis (and microscopy, as appropriate)	X									

# Table 1. Overall Schedule of Activities Screening to Period 5

Visit Identifier Abbreviations used in this table may be found in	Screening	Peri (DE		Period 2 (ROSU only)		Period 3 7081532	only)		iod 4 1532 + DE)	Period 5 (PF-07081532
Appendix 9		,	• •		,		• *	`	•	+ ROSU)
Day in Study Period a	-28 to -2	-l	1-2	1-4	1	2-7	8	1-4	5	1-4
Days in Study b	-28 to -2	-1	1-2	3-6	7	8-13	14	15-18	19	20-23

- Day relative to start of dosing Day 1 of that Period.
- Day relative to first dose of investigational product (DE) on Day 1 of Period 1.
- Complete physical exam at Screening, otherwise, brief exam if findings during previous exam or new/open AEs, if appropriate, at investigator discretion.
- d. Participants will be screened for COVID-19 according to local procedures prior to being admitted to the clinic for confinement in Period 1. Subsequent testing will also be done according to local procedure if participants develop COVID-19 like symptoms. See also Section 8.3.5 (COVID-19 Specific Assessments). If a participant tests positive for SARS-CoV-2 infection, they will be discharged from the study.
- e. Includes BP and PR predose.
- Dosing to occur QD with breakfast as specified in Section 6.1.1.
- g. The rosuvastatin PK sample is to be collected predose (0 hr) on Day 1 of Period 3.
- Collection following fasting duration specified in Section 5.3.2.
- FSH for female participants to confirm PM status only. Serum β-hCG for all WOCBP; test result should confirm no pregnancy prior to dosing.

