### CC

- k. Participants may undergo random urine drug testing at the discretion of the investigator.
- Assessments to be done on Day 1 of Periods 1, 3, and 5 and prior to IP administration on all days indicated.

Table 2. Overall Schedule of Activities Period 6 to ET

Visit Identifier Abbreviations used in this table may be found in Appendix 9			riod 6 81532 only	7)	Perio (PF-070) DI	81532 +	(PF-07	riod 8 7081532 + OSU)	F/U Visit q	F/U Contact Telephone	ET
Day in Study Period a	1-5	6-10	11-15	16-20	1-4	5	1-4	5	7-10	28-35	-
Days in Study b	24-28	29-33	34-38	39-43	44-47	48	49-52	53 f	59-62	80-87	-
Outpatient visit (after ≥10 hr fast)									X		
Physical exam											Χ°
Review contraception use - WOCBP Only (Section 5.3.1)									X	X	
Review drug, alcohol/tobacco use									X		
COVID-19 screening d											
C-SSRS and PHQ-9°	X			X				X	X		X
Review prior or concomitant treatments	$\rightarrow$	$\rightarrow$	$\rightarrow$	$\rightarrow$	_	<del>}</del>	$\rightarrow$	X	X	X	
AE monitoring	→	$\rightarrow$	$\rightarrow$	$\rightarrow$	_	>	$\rightarrow$	X	X	X	
Inpatient stay at CRU	→	$\rightarrow$	$\rightarrow$	$\rightarrow$	_	<del>}</del>	+	Xi			
Body weight g	X		X	X				Xi	X		X
Supine 12-lead ECG		Xh						$X^{i}$			X
Single, supine vital signs assessment	X		X	X				Xi	X		X
Blood Sampling for: k											
- Chemistry	X 			X 				X i	X		X
- Calcitonin, amylase, lipase				$X^1$				Xi			X
- Free T4, TSH, lipid panel, total bile acids								Xi	1		X
- Hematology/HbA1c				X 				Xi	X		X
- Serum pregnancy test m								Xi			
Rosuvastatin administration							Table 4				
DE administration					Table 3						
PF-07081532 administration n	→	→	→	→	1	Table 5	Table 4				
PF-07081532 PK						1					X
Rosuvastatin PK	Χ°						1	Table 4			
Dabigatran PK					Table 3						
CCI											
Urine Sampling for:											
- Urine drug test p											
- Urinalysis (and microscopy, as appropriate)											X

a. Day relative to start of dosing Day 1 of that Period.

b. Day relative to first dose of investigational product (DE) on Day 1 of Period 1.

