# Table 2. Overall Schedule of Activities Period 6 to ET

Visit Identifier Abbreviations used in this table may be found in Appendix 9			riod 6 81532 only	·)	Perio (PF-0708 DF	81532 +	(PF-07	riod 8 7081532 + OSU)	F/U Visit q	F/U Contact Telephone	ET
Day in Study Period a	1-5	6-10	11-15	16-20	1-4	5	1-4	5	7-10	28-35	-
Days in Study b	24-28	29-33	34-38	39-43	44-47	48	49-52	53 f	59-62	80-87	-

- c. Brief exam if findings during previous exam or new/open AEs, if appropriate, at investigator discretion.
- d. Participants will be screened for COVID-19 according to local practice prior to being admitted to the clinic for confinement in Period 1. A subsequent test will be done according to local procedure if participants develop COVID-19 like symptoms. See also Section 8.3.5 (COVID-19 Specific Assessments). If participants test positive for SARS-CoV-2 infection, they will be discharged from the study.
- e. C-SSRS and PHQ-9 will be administered in Period 6 on Days 5 and 19, and in Period 8 on Day 5 (discharge from CRU).
- f. Discharge from CRU.
- g. Body weight to be obtained on Days 5, 12 and 19 in Period 6.
- h. ECG to be obtained on Day 10 of Period 6.
- i. Assessments to be obtained on Day 5 of Period 8 prior to D/C from the CRU.
- j. Includes BP and PR predose; to be obtained on Days 5, 12 and 19 in Period 6.
- k. Collection following fasting duration specified in Section 5.3.2.
- 1. Chemistry to be obtained on Days 1 and 20 in Period 6; calcitonin, amylase, lipase and hematology to be obtained on Day 20 in Period 6.
- m. Serum β-hCG for all WOCBP
- n. Dosing to occur QD with breakfast. Note that there is no PF-07081532 administration on Study Day 53 or anytime thereafter.
- o. The rosuvastatin PK sample is to be collected predose (0 hr) on Day 1 of Period 6.
- p. Participants may undergo random urine drug testing at the discretion of the investigator.
- q. The follow-up visit 7-10 days after the last dose of study intervention (Period 8, Day 4) can be on-site or via telephone call. Whether the follow-up visit is on-site or via telephone call is at the discretion of the Investigator. Regardless of location (ie, on site or telephone call), contraception use, drug, alcohol/tobacco use, concomitant medications and AEs must be reviewed/assessed as appropriate.

Table 3. Schedule of Activities – Period 1 (DE ONLY), Period 4 (DE + PF-07081532 80 mg QD) and Period 7 (DE + PF-07081532 260 mg QD)

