## 7. DISCONTINUATION OF STUDY INTERVENTION AND PARTICIPANT DISCONTINUATION/WITHDRAWAL

#### 7.1. Discontinuation of Study Intervention

It may be necessary for a participant to permanently discontinue study intervention. Reasons for permanent discontinuation of study intervention include the following:

- Criteria for a potential Hy's law case are met (see Appendix 6).
- Intent to become pregnant or pregnancy confirmed by serum  $\beta$ -hCG testing.
- Safety or tolerability concern arises, in particular if not responsive to symptomatic management, dosing with study intervention may be stopped in an individual participant at investigator discretion.
- Based on mental health assessment as outlined in Section 8.3.8.3, should be discontinued from dosing at investigator discretion.
- If the criteria for permanent discontinuation are met, the site should notify the sponsor Medical Monitor or sponsor Clinician.
- Positive SARS-CoV-2 test (see Section 8.3.5).
- Potential or confirmed AKI (see Section 7.1.1).

Note that discontinuation of study intervention does not represent withdrawal from the study. If study intervention is permanently discontinued, the participant should remain in the study to be evaluated for an ET visit. See the SoA for data to be collected at the time of discontinuation of study intervention and follow-up for any further evaluations that need to be completed.

In the event of discontinuation of study intervention, it must be documented on the appropriate CRF/in the medical records whether the participant is discontinuing further receipt of study intervention or also from study procedures, post-treatment study follow-up, and/or future collection of additional information.

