# 10.4.2. Female Participant Reproductive Inclusion Criteria

The criteria below are part of Inclusion Criterion 1 (Age and Sex; Section 5.1) and specify the reproductive requirements for including female participants. Refer to Section 10.4.4 for a complete list of contraceptive methods permitted in the study.

A female participant is eligible to participate if she is not pregnant or breastfeeding and at least 1 of the following conditions applies:

• Is not a WOCBP (see definition in Section 10.4.3).

OR

• Is a WOCBP and agrees to use a highly effective contraceptive method (failure rate of <1% per year) during the intervention period and for at least 28 days after the last dose of study intervention, which corresponds to the time needed to eliminate any reproductive safety risk of the study intervention(s). If a highly effective, user-dependent method is chosen, she agrees to concurrently use an effective barrier method of contraception. The investigator should evaluate the effectiveness of the contraceptive method in relationship to the first dose of study intervention.

The investigator is responsible for review of medical history, menstrual history, and recent sexual activity to decrease the risk for inclusion of a woman with an early undetected pregnancy.

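### Section 8.3.7 requires an end-of-study pregnancy test, but after Day -1 the schedule of activities shows only one, at Period 8 Day 5; early stoppers have no scheduled exit test, and completers have none at the end of study that Section 4.4 defines

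*Protocol*

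**What the plan says.** Protocol Section 8.3.7 gives two sources for the timing of tests. Routine testing follows the schedule: "Pregnancy tests will be performed in WOCBP at the times listed in the SoA". Section 8.3.7 then adds tests when a cycle is missed during active treatment, "or when potential pregnancy is otherwise suspected) and at the end of the study". It does not say which visit the last phrase means.

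The schedule of activities (Section 1.3) has a row labelled "Serum pregnancy test" in both overall tables. Table 1 marks it at Screening and Day -1. Table 2 marks it once, under Period 8 Day 5, with the footnote "Assessments to be obtained on Day 5 of Period 8 prior to D/C from the CRU". The cells for the follow-up visit, the telephone contact and ET are empty.

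For permanent discontinuation of study intervention, Section 7.1 says that "the participant should remain in the study to be evaluated for an ET visit" and refers to the schedule for the data to collect. Section 7.2 does the same for the early discontinuation visit.

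Two other passages bear on timing. Section 10.4.2 requires contraception during the intervention period and "for at least 28 days after the last dose of study intervention", and ties that interval to the elimination of reproductive risk. Section 4.4 places the end of the study at the telephone contact, 28 to 35 days after the last dose.

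**The concern.** The text requires a test that the schedule does not show. Sites usually build visit worksheets and laboratory orders from the schedule, and Sections 7.1 and 7.2 direct them there for anyone who leaves early. A woman who stops before Period 8 Day 5 would then leave with no scheduled pregnancy test since Day -1.

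The check concerns fetal exposure. Section 4.2.1 states that no human reproductive safety data exist for PF-07081532, while adding that its pharmacology gives no reason to suspect teratogenicity. Section 8.4.5.1 requires exposure during pregnancy to be reported within 24 hours of the investigator becoming aware of it, and that depends on detection. The primary pharmacokinetic analysis is not affected.

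**Working it through.** The plan gives no figure to reproduce. The check sets the passages side by side and counts days.

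**1. Is the blank ET cell real?** The Table 2 row has 11 cells: 4 for Period 6, 2 for Period 7, 2 for Period 8, then follow-up visit, telephone contact and ET. The only mark is in the eighth, Period 8 Day 5. Neighbouring rows (chemistry; calcitonin, amylase and lipase; thyroid, lipids and bile acids; hematology and HbA1c) do carry an ET mark, as do urinalysis and the PF-07081532 sample. The row is intact and the cell is empty; it is not redacted.

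**2. Women who stop before Period 8 Day 5.** Inputs: last scheduled test on Day -1 (Table 1); first dose of any study drug on Day 1; PF-07081532 on Study Days 7 to 52 (Table 8). There is no Day 0, so a woman stopping on Study Day d was last tested d days earlier.
- Stop on Day 7, the first PF-07081532 dose: 7 days.
- Stop on Day 52: 52 days.

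These are elapsed study days. Dosing days are fewer: 52 − 7 + 1 = 46 days of PF-07081532, plus single doses of dabigatran etexilate (Day 1) and rosuvastatin (Day 3) before it starts, gives at most 48. SAP Section 2.1 says the study was shortened by 6 days. If all 6 fall before the last dose (an assumption), the longest interval is 52 − 6 = 46 study days. The empty cells are unaffected.

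**3. Completers.** Last dose is on Day 52 (Period 8 Day 4) and the last scheduled test on Day 53.
- Test relative to last dose: 53 − 52 = 1 day after.
- End of the 28-day minimum in Section 10.4.2: 52 + 28 = Day 80.
- Final contact in Table 2: Days 80 to 87.
- Last test to the end of that minimum: 80 − 53 = 27 days.
- Last test to the Section 4.4 endpoint: 27 to 34 days (87 − 53 = 34).

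**4. Does any reading of the end of the study reconcile text and schedule?**
- Period 8 Day 5: completers have the test, but early stoppers never reach that visit.
- ET for early stoppers: the cell is blank.
- The telephone contact, as in Section 4.4: no test is scheduled there for anyone.

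No reading makes the text and schedule agree for both groups.

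**5. How many women?** Section 9.5 plans about 24 enrolled for about 16 evaluable completers: 24 − 16 = 8, or one third. The share of childbearing potential is not given. Assuming 25% to 50%, 8 × 0.25 = 2 and 8 × 0.50 = 4; the ceiling is 8.

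**The case against.** The strongest reply is that the blank cell does not cancel Section 8.3.7. Section 1.3 calls the schedule an overview and refers to the assessments section for detail, and Section 8.3.7 presents the end-of-study test as additional to the scheduled ones. A site that puts the text first would test. This stands, so a reader should not infer that every woman who stops early will leave untested. What is missing is a scheduled exit test. The reply does not remove the conflict: Section 8.3.7 defers to the schedule for routine times, Section 8.1 makes adherence to the schedule essential, and Sections 7.1 and 7.2 refer to it for the exit visit.

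Existing safeguards also count. Two negative tests are required before dosing, participants are confined from Day -1 to Day 53, highly effective contraception is required, and participants must call if pregnancy is suspected (Section 5.3.1). ET lacks a contraception review, but both follow-up contacts have one and those who stop treatment remain in follow-up, so the documents do not support a claim that contraception goes unreviewed after early exit. The missed-cycle rule covers part of the case of a conception too recent to show on Day -1, but it is worded for active treatment, and a woman who stops in the first weeks may leave before a cycle is missed.

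The expected number of pregnancies is very small. With 4 women, the contraceptive failure rate of under 1% per year in Section 10.4.2, and 54 inpatient days plus 28 days, the expectation is below 4 × 0.01 × 82/365 = 0.009. That limits the size of the concern. It does not cover a conception before contraception took effect.

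**Conclusion.** The conflict stands. Section 8.3.7 requires an end-of-study test; the schedule shows none at ET or at either follow-up contact. For a woman who stops before Period 8 Day 5, the last scheduled test precedes all dosing, by up to 52 study days under the protocol schedule. Completers are last tested 1 day after the last dose, 27 to 34 days before the study ends under Section 4.4.

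Three stronger readings are not supported:
- The 52 days are not 52 days of dosing; the most possible is 48.
- The 2 to 4 women rest on an assumed share of an allowance for non-completion. They are not a forecast of early exits, still less of pregnancies.
- Treating Period 8 Day 5 or ET as the self-evident end of the study conflicts with Section 4.4.

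That the ET visit falls inside the 28-day window is an inference from Sections 7.1 and 7.2, which tie it to discontinuation; Table 2 gives it no study day. The point merits correction because it is a participant-safety check and almost free to settle, not because many pregnancies are expected.

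**What to change.** Reconcile Section 8.3.7, Table 2 (ET and follow-up columns) and Section 4.4, so that the schedule shows the end-of-study pregnancy test that Section 8.3.7 requires for completers and for early stoppers, and Section 8.3.7 names the visit it means for each group. If the phrase is not meant in the Section 4.4 sense, say so.

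Which visit to use is for the sponsor to decide. Two facts in the documents bear on feasibility. Blood is already drawn at ET, so a test placed there needs one added assay for the few women of childbearing potential who stop early. The 7 to 10 day follow-up may be done by telephone at the investigator's discretion, and the final contact is by telephone, so neither guarantees a sample as planned.

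The document cost is a mark or footnote in Table 2, a sentence in Section 8.3.7 and, if needed, a cross-reference to Section 4.4.
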